	Study 1	Study 2	mg	mg	mg	mg
	n=309	n=306	Study 1	Study 2	Study 2	Study 2
			n=310	n=308	n=308	n=306
Any AE	105	100	116	117	121	117
	(34%)	(33%)	(38%)	(38%)	(39%)	(38%)
Any SAE	7 (2%)	7 (2%)	3 (1%)	2 (1%)	3 (1%)	3 (1%)
Nasopharyngitis	20 (6%)	16 (5%)	20 (6%)	21 (7%)	13 (4%)	16 (5%)
Headache	12 (4%)	11 (4%)	19 (6%)	16 (5%)	15 (5%)	12 (4%)
Somnolence	6 (2%)	4 (1%)	5 (2%)	11 (4%)	10 (3%)	6 (2%)

Choice of dosing days/times:

We will give 50 mg daridorexant (25 mg to those on moderate 3A4 inhibitor, as above) or placebo 8-10 PM on the first 3 postop nights and evaluate delirium on each of the days following administration—*i.e.*, POD 1–3. We give study agent the night prior to each day's assessment because **the prior night's sleep directly impacts cognition the next day**. Sleep restriction causes neurocognitive impairment the following day with the most pronounced effects in sustained attention (vigilance). We choose 8-10 PM because daridorexant's T_{max} is 1–2 hr. This (1) allows time for its soporific effect and (2) is early enough to mitigate next-morning sedation). S2,67,68 For any subject still intubated during the 8-10 PM window, we will allow for administration up to midnight in the event that they are extubated prior to midnight. This is to maximize the likelihood of administration on the first postoperative night.

Justification and safety information if FDA approved drugs will be administered for non-FDA approved indications or if doses or routes of administration or subject populations are changed:

On September 18, 2024, we received a determination from the US FDA that our proposed trial "meets all meets all of the requirements for exemption from the IND regulations and, therefore, an IND is not required to conduct [this] investigation." See attached document, "FDA exemption determination (24-09-18)."

Medication and matching placebo will be stored by IDS, who will be responsible for randomization subjects to study arms, keeping records on medication storage, and ensuring timely dispensing.

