8. STUDY PROCEDURES

See Table 5 below for the Schedule of Activities

Table 5 - Schedule of activities

Assessment	Screenin	Baseline	PON 1-3	POD 1-3	POD 3-7
	g	(1 hr)	(with	(15 min)	(15 min)
	(15 min)		bedtime		
			meds)		
Verbal consent	X				
CAGE-AID	X				
Written consent		X			
Demographics		X			
CCI		X			
Medication list		X			
Cognition/function					
TICS	X				
MoCA		Full, v8.1			
Lawton		X			
CDR		X			
WTAR		X			
Delirium					
3D-CAM	X			X	Χ [†]
DRS-R98				X	X [†]
Mental health					
PHQ-9		X			
GAD-7		X			
Sleep-related					
PSQI		X			
ESS		X			
RCSQ				X	X [†]
Medication administration			X		
AEs/SAEs					
Questionnaire		X		X	
Chart review*				X	X [†]
Subject to guess whether they received				POD 3	
daridorexant or placebo	 				

Abbreviations: **3D-CAM**, 3-Minute Diagnostic Interview for Confusion Assessment Method; **CAGE-AID**, CAGE [acronym for "Cut-down, Annoyed, Guilt, Eye-opener"] adapted to include drugs; **CCI**, Charlson comorbidity index; **CDR**, Clinical Dementia Rating; **DISH**, Depression Interview and Structured Hamilton; **DRS-R98**, Delirium Rating Scale, Revised 98; **ESS**, Epworth Sleepiness Scale; **GAD-7**, 7-item Generalized Anxiety Disorder scale; **Lawton**, Lawton Instrumental Activities of Daily Living; **MoCA**, Montreal Cognitive Assessment; **PHQ-9**, 9-item Patient Health Questionnaire; **POD**, postoperative day; **PON**, postoperative night (*i.e*, the night of POD 0 [the day of surgery] is defined as PON 1); **PSQI**, Pittsburgh Sleep Quality Index; **RCSQ**, Richards-Campbell Sleep Questionnaire; **TICS**, Telephone Interview for Cognitive Status; **WTAR**, Wechsler Test of Adult Reading

Screening procedures:

As indicated under **7. CONSENT PROCESS** above, consent will involve two steps—a verbal consent for study eligibility screening and, subsequently, signed consent. When obtaining verbal consent, we will

^{*}For evidence of adverse events, documentation of delirium, potential sleep confounds

[†]Daily assessments for delirium and sleep will continue if the subject is delirious on POD 3, until delirium resolves.

Version date: 2/3/2025

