indicate to study prospects that the eligibility questions take 5–10 minutes. We indicate that we keep responses to screening questions, even for those who don't end up taking part, so, as a result and explain that we do not record personally identifying information during the screening process. Before proceeding with the remainder of the eligibility assessment, we also ask the prospective subject to affirm the availability of a study partner should they participate in the study.

Study duration:

Study subjects will participate from the initial screening evaluation prior to surgery, which is usually 1–2 weeks prior to scheduled surgery, through the third postoperative day after surgery (*note*: as in the following paragraph, assessments may be continued past POD 3 if the subject is found to have delirium on POD 3). Most subjects, then, will be enrolled in the study for roughly 2 weeks. However, the duration of study participation will be dependent on the scheduling of preoperative anesthesiology visit in relation to date of surgery.

Choice of POD and assessments for delirium:

We assess delirium on POD 1–3 with the DRS-R-98 as validated based on clinical interview under the supervision of a psychiatrist. We omit delirium assessment on POD 0 because (1) patients are intubated and sedated until the evening of POD 0 and (2) to exclude emergence delirium (*n.b.*, a distinct physiological event due to anesthetic effects¹⁰⁰). With one exception (see below), we restrict delirium assessments to POD 3 because (1) patients are often discharged on POD 3 or 4, (2) postop delirium peaks on POD 2 and 3, coincident with the peak of postop inflammation, ^{101,102} and (3) this allows a commensurate 3-day period across subjects to evaluate for delirium during the days of greatest risk. We use DRS-R-98 as it is well validated and the most robust tool for characterizing delirium phenomenology. ^{1,16,17,20,21,103} Regarding the exception referenced above: to determine delirium duration in all subjects, we continue to perform daily delirium assessments for any subject positive for delirium on POD 3 until no longer positive. Regardless of whether delirium assessments continue beyond POD 3, subjects will still receive study drug for only the first three nights after surgery.

Number of visits:

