Subjects will have four (or up to a maximum of 8, if a person continues to score positive for delirium on POD 3 through POD 6) in-person visits with study personnel (see **Figure 1**, Timeline of Study Assessments in Section 4. STUDY DESIGN).

Blinding, including justification:

Blinding of study staff, clinical staff, and the patient is critical for this trial, which test whether daridorexant prevents postoperative delirium.

Justification of why subjects will not receive routine care or will have current therapy stopped:

Subjects will receive routine surgical and postoperative care. This trial adds exposure only to daridorexant or placebo to test whether daridorexant prevents delirium. No current therapy will be stopped or modified.

Justification for inclusion of a placebo group:

The use of a placebo treatment is essential to understand the effects (both positive and negative) of daridorexant exposure. Placebo comparison is the only way that we can understand what is likely due to daridorexant and what is not.

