Each adverse event—whether observed by the PI or elicited from or volunteered by the subject—will be documented. Each adverse event will include a brief description of the experience, the date of onset, the date of resolution, the duration and type of experience, the severity, the nature of any potential relationship to study assessments, contributing factors, and any action taken with respect to the assessments. Any such adverse event will be reported to the Data and Safety Monitoring Advisory Council (see 16. Data and Safety Monitoring Plan).

Responsibilities for reporting serious adverse events:

The PI will record all serious adverse experiences that occur during the study period in the appropriate source documents and/or adverse events log as applicable. The timeframe for adverse event reporting will begin from the time of study enrollment to the final study assessment on POD 3 (or on a subsequent postoperative day for those with delirium on POD 3).

Steps taken to minimize risk:

We will adhere to the exclusion criteria listed above which will help avoid the recruitment of patients most at risk of side effects and adverse consequences. Patients will be interviewed each day for any side effects and the medical records will be reviewed and the data collected for Aim 4 of this study.

Risks pertaining to clinical assessment:

The risks pertaining to clinical assessment (neuropsychological testing and questionnaires) are anticipated to be no more than minimal. If the patient exhibits any distress or hesitation in answering specific

questions or completing a questionnaire in general, the evaluation will be suspended and the subject asked whether they wish to either take a break, skip a given section, or withdraw from the study. The PI [name] is a board-certified psychiatrist with clinical expertise in mental health evaluation. If he is conducting the assessment, he will use his medical judgment to determine whether to suspend evaluation or skip portions of the interview. If study personnel are conducting the evaluation, they will be instructed to contact [name] to join the interview and conduct additional assessment as necessary to determine whether the interview should be suspended or modified.

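### AE/SAE capture stops the day after the last dose unless the subject is delirious on POD 3, so post-dose safety follow-up depends on the outcome the drug targets, and later SAEs are not systematically captured

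*Protocol*

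**What the plan says.** **Dosing.** Section 4.2 gives study drug "8-10 PM on the first 3 postop nights". The notes to Table 5 (Section 8) state that "the night of POD 0 [the day of surgery] is defined as PON 1". The three doses therefore fall on the evenings of POD 0, POD 1 and POD 2.

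**Reporting window.** Section 9 (responsibilities for reporting SAEs) opens AE reporting at enrollment and closes it at "the final study assessment on POD 3 (or on a subsequent postoperative day for those with delirium on POD 3". Under study duration, Section 8 has participation run "through the third postoperative day after surgery", with the same exception for delirium.

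**Table 5.** The AE questionnaire is marked at baseline and POD 1-3. Chart review, footnoted "For evidence of adverse events, documentation of delirium, potential sleep confounds", is marked on POD 1-3 and, with a dagger, on POD 3-7. The dagger reads "Daily assessments for delirium and sleep will continue if the subject is delirious on POD 3, until delirium resolves".

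**End of the extension.** Section 8 says in one place that "we continue to perform daily delirium assessments for any subject positive for delirium on POD 3 until no longer positive". In another it limits in-person visits to four, or "up to a maximum of 8, if a person continues to score positive for delirium on POD 3 through POD 6".

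**Role of safety.** Section 4 names feasibility and safety as the primary outcomes. Aim 4 is to document all potential AEs and SAEs. Section 17 plans to collect these data and states no comparison between arms. Section 16 has the DSMB review the data after 6 and after 12 completers.

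**The concern.** How long a subject is observed for safety after the last dose is decided by delirium status on POD 3. That status arises after randomization, and the study drug is intended to change it. If the arms differ in POD 3 delirium, the arm with more of it is watched longer, and crude AE and SAE counts by arm no longer cover equal time.

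The second consequence matters more. The SAE definition in Section 9 includes prolonged hospitalization and persistent disability. Section 8 notes that discharge often occurs on POD 3 or 4, so such outcomes may not be recognizable at the POD 3 assessment. For subjects not delirious that day, no scheduled collection follows. A later analysis plan can restrict a table to POD 3, but it cannot recover SAEs that were never collected. The descriptive safety data, the DSMB reviews and the follow-on trial that this study is meant to inform are what is at stake.

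**Working it through.** **1. Visit count (the protocol's own figure).** Baseline + POD 1-3 = 1 + 3 = 4. Adding POD 4, 5, 6 and 7 for a subject positive from POD 3 through POD 6 gives 4 + 4 = 8. Both stated figures reproduce, and the maximum of 8 implies a last visit on POD 7.

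**2. Time from last dose to close of window.** The last dose is at 8-10 PM on POD 2. If the POD 3 assessment falls between 8 AM and 5 PM (assumed), the gap is 10 to 21 hours.

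**3. Extra observation by arm.** Inputs:
- 6 completers per arm (12 completers, blocks of six, Sections 4.1 and 16).
- Extra days d = 1 to 4 for a subject delirious on POD 3 (4 is the most that the visit maximum allows).
- POD 3 prevalence P: not given, so assumed. The protocol's 30% is incidence after SAVR at the institution (Section 4.1), not POD 3 prevalence, so a halved case is run as well. Halving by the drug is also an assumption.

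Formulas: mean days on a POD 1-3 base = 3 + d × P; extra placebo person-days per 6 = 6 × d × (difference in P).

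| P placebo vs drug | d | Mean days | Ratio | Extra person-days |
|---|---|---|---|---|
| 0.30 vs 0.15 | 1 | 3.30 / 3.15 | 1.048 | 0.9 |
| 0.30 vs 0.15 | 4 | 4.20 / 3.60 | 1.167 | 3.6 |
| 0.15 vs 0.075 | 1 | 3.15 / 3.075 | 1.024 | 0.45 |
| 0.15 vs 0.075 | 4 | 3.60 / 3.30 | 1.091 | 1.8 |

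The extra person-days all come after the last dose. The percentages (2-17%) do not describe post-dose time alone, because POD 1 and most of POD 2 in their base precede the last dose. Counting POD 0 makes the base 4 days: 4.15/4.075 = 1.018 to 5.20/4.60 = 1.130, or 2-13%. Counting the stated window from enrollment, with 7 to 14 preoperative days assumed from the 1-2 weeks in Section 8, gives 18.15/18.075 = 1.004 to 12.2/11.6 = 1.052, or 0.4-5%.

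The 17% also needs every POD 3 case to stay positive through POD 6. If delirium persists from day to day with probability q = 0.5 to 0.7 (assumed), mean extra days up to POD 7 are 1 + q + q² + q³ = 1.875 to 2.533. The excess on the POD 1-3 base is then 4-11% across both prevalence cases.

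**4. Effect on AE counts.** Spurious placebo excess = AE rate × extra person-days, at an assumed equal rate of 0.02 to 0.10 per person-day. For 30% vs 15%:
- d = 2 (6 × 2 × 0.15 = 1.8 person-days): 0.04 to 0.18 events.
- d = 4 (3.6 person-days): 0.07 to 0.36 events.

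An extreme case of 50% vs 0% with d = 4 gives 6 × 4 × 0.50 = 12 person-days and at most 0.10 × 12 = 1.2 events.

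**5. Text set side by side.**
- *Method in the extension:* Table 5 marks chart review but no AE questionnaire on POD 3-7. Section 9 has patients interviewed daily for side effects, and AE data collected on each postoperative day of enrollment.
- *End of the extension:* the visit maximum and the POD 3-7 heading stop at POD 7. The dagger and the delirium-assessment text continue until resolution. Without a cap, q⁴ = 0.06 to 0.24 of POD 3 cases would be assessed after POD 7.

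**The case against.** The strongest objection is that no planned analysis is harmed. Section 17 states no AE comparison, and onset dates are recorded, so an equal window through POD 3 can be built from data already planned. AEs must be attributable to the drug or the assessments. With the 8-hour half-life in Table 1 of the protocol, about 4-5% of drug remains by 8 AM on POD 4 (34-36 hours after dosing; 0.5^(34/8) = 0.053, 0.5^(36/8) = 0.044). The extension also has a sound stated purpose, which is to measure delirium duration. All of this stands, and it is why the bias in counts is small.

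Late SAEs are said to be covered because each AE record includes a resolution date and treating teams must report potential AEs and SAEs to the PI. This stands only in part. Nothing says that AEs open at POD 3 are followed, or until when. The AE definition covers events arising during the study, which ends on POD 3 for most subjects, so a later event may fall outside the reporting duty. It is also fair that review to discharge would often add only a day or so.

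A reader might infer that the safety comparison is materially tilted toward daridorexant, or that up to 17% more observation means 17% more events. The documents support neither. There is no stated comparison, the percentage depends on the chosen base and on assumed prevalences, and the expected distortion is usually well under one event.

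**Conclusion.** The point holds as a modest defect in data collection. By the protocol's own dosing and reporting rules, safety capture closes the day after the last dose, and is extended only by an outcome the drug is meant to change.

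The resulting imbalance is 0.45 to 3.6 post-dose person-days per 6 completers under the assumed prevalences and 1 to 4 extra days. That is 2-17% on a POD 1-3 base and less on a longer one. With equal true POD 3 delirium rates, no imbalance is expected. The effect is confined to descriptive safety data and the DSMB reviews.

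The more material part is the lack of systematic capture, in non-delirious subjects, of SAE outcomes that emerge after POD 3. The documents give no figure for how often that would happen, so its size is unknown. The two inconsistencies over the POD 3-7 period are real but minor.

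**What to change.** 1. In Section 9, state that AE/SAE summaries by arm use one window for all dosed subjects, first dose through POD 3, whatever their delirium status. List later events separately with days observed. This needs no new data.
2. In Section 9 and Table 5, extend the existing chart review to hospital discharge for every dosed subject, for SAEs and for AEs still open at POD 3. State that these data serve completeness and not comparison of arms, because time to discharge itself depends on delirium (Section 2, A.2, links it to longer stays).
3. Reconcile the POD 3-7 column of Table 5 (chart review, no AE questionnaire) with the daily interview and daily AE collection in Section 9.
4. Reconcile the maximum of 8 visits and the POD 3-7 heading with the text that continues assessments until delirium resolves.

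The cost is wording in Section 9 and Table 5, a matching edit to the study-duration text in Section 8, and a brief extra chart review for up to 16 inpatients. Items 1 and 2 add no visits. Items 3 and 4 are minor edits.

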
Plan for breaking the blind for a subject

If a patient has a medical emergency that requires immediate clinical care for stabilization, including angioedema, anaphylaxis, attempted suicide, or any other condition that is considered—in the opinion of the PI or the primary medical team—as potentially attributable to daridorexant, we will contact the IDS pharmacist to identify whether the patient has received daridorexant or placebo. If this occurs, the subject will be withdrawn from the study, and this will be reported to the RSRB and DSMB.

Legal risks such as the risks that would be associated with breach of confidentiality:

As with any study incorporating research into clinical care, there is a small but real risk of unintentional release of HPI. We will make every effort to secure data and study records under double lock/key and encryption in keeping with institutional standards to prevent this from occurring.

Version date: 2/3/2025

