3. ADMINISTRATIVE ORGANIZATION

This single-site trial represents a collaboration among the Department of Psychiatry, Department of Anesthesiology, and the Department of Surgery, Division of Cardiac Surgery, Randomization with a block size of six and drug dispensing will occur through Investigational Drug Services (IDS) at Strong Memorial Hospital (SMH). Prospective subjects may be identified in the hospital while awaiting surgery, at the time of outpatient evaluation by a cardiac surgeon, or in conjunction with anesthesiology during pre-surgical history and physical, typically performed at the Center for Perioperative Medicine.

Version date: 2/3/2025

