6.2 Post-Marketing Experience

The following adverse reactions have been identified during post-approval use of QUVIVIQ. Because these reactions are reported voluntarily from a population of uncertain size, it is not always possible to reliably estimate their frequency or establish a causal relationship to drug exposure.

Psychiatric disorders: Nightmares or abnormal dreams

Immune system disorders: Hypersensitivity (including angioedema, rash, urticaria)

Version date: 2/3/2025

Safety assessments:

In this trial, we obtain demographics and baseline assessment of medical morbidity, medications, cognitive status, and self-report sleep & mental health. Obtaining such information does not entail significant foreseeable risk beyond limited risk of psychological distress or questionnaire fatigue. As we will be completing the 9-question Patient Healthcare Questionnaire (PHQ-9), which assesses suicidal ideation, we have developed a safety plan for anyone who answers positively to question 9 on the PHQ-9 (see Steps taken to minimize risk below).

Adverse event definition:

This is an observational study of medically and surgically ill patients undergoing open-heart surgery, and this population—independent of this study—is at significant risk for a range of medical and surgical complications because of their underlying heart disease, open-heart surgery, and care provided during the perioperative period. In this study, we define an adverse event as any symptom, sign, illness, or experience that develops or worsens during the study that is reasonably attributable to the study assessments or receipt of daridorexant.

Serious adverse event:

A serious adverse event is defined as any adverse event resulting in any of the following:

- Sleep paralysis (inability to move or speak when going to sleep or waking up)
- Cataplexy (discrete episode of muscle weakness, typically associated with strong emotion)
- Complex behaviors while asleep that pose danger to the patient or others (e.g., sexually inappropriate acts)
- Angioedema or anaphylactic reaction to daridorexant
- Death/suicide
- Prolongation of existing hospitalization
- Persistent or significant disability or incapacity
- Medical or surgical intervention required to prevent permanent impairment or damage

Recording adverse events:

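### An emergency code break gives the study team the arm before adverse event status has to be fixed, and the AE definition depends on receipt of daridorexant

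*Protocol*

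**What the plan says.** Protocol section 8 (Blinding, including justification) sets the standard: "Blinding of study staff, clinical staff, and the patient is critical for this trial".

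Protocol section 9 (Plan for breaking the blind for a subject) covers emergencies that need immediate stabilising care. It names angioedema, anaphylaxis and attempted suicide, and adds any other condition "considered—in the opinion of the PI or the primary medical team—as potentially attributable to daridorexant". In such a case "we will contact the IDS pharmacist to identify whether the patient has received daridorexant or placebo". The consequence is the same in either arm: "If this occurs, the subject will be withdrawn from the study, and this will be reported to the RSRB and DSMB".

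Protocol section 9 (Adverse event definition) counts a symptom, sign, illness or experience as an AE only if it is one "that develops or worsens during the study that is reasonably attributable to the study assessments or receipt of daridorexant". The next subsection makes SAEs a subset: "A serious adverse event is defined as any adverse event resulting in any of the following". One item on the SAE list is angioedema or anaphylaxis caused by daridorexant.

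The AE record described under Recording adverse events has an entry for relationship to the study assessments. It names none for relationship to the study drug. The PI records SAEs (section 9) and is the Data and Safety Monitor, advised by an independent DSMB (section 16). Safety is a primary outcome together with feasibility (section 4).

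**The concern.** Whether an event counts as an AE is a causal judgement, and the definition ties that judgement to the active drug rather than to the study agent. While the assessor is blinded, this does little harm: a placebo subject might have received daridorexant, so the event can be judged attributable. Once the assessor knows the subject received placebo, attribution to daridorexant is ruled out, and only attribution to the study assessments remains. For an emergency such as angioedema, that route is remote.

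The code-break procedure gives this knowledge to the people who classify events, and does so for the most serious ones. The protocol has no step that fixes the classification first. At stake is whether the AE and SAE counts by arm, which are meant to inform the follow-on trial, were formed in the same way in both arms.

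**Working it through.** The protocol states no figure on this point, so the check is textual, followed by one illustration.

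**Step 1: who learns the arm.** The code-break paragraph is written in the first person plural, so the study team makes the request and receives the answer. Nothing limits disclosure to the treating clinician.

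**Step 2: what has been judged by then.** For events not named in the list, the trigger is an opinion, from the PI or the primary medical team, that the event is *potentially* attributable to daridorexant. The AE definition asks for *reasonable* attribution. The second test is stricter, so passing the first does not settle it.

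**Step 3: whether the earlier opinion is captured.** The AE record lists relationship to study assessments but not to study drug, so the opinion formed before the code break has no listed place. The record also asks for the resolution date, the duration and the action taken. In an emergency these would usually be completed after the code is open.

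**Step 4: what the definition yields once the arm is known.** Take the same emergency, unrelated to the study assessments:

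| State of knowledge | Subject on daridorexant | Subject on placebo |
|---|---|---|
| Assessor blinded | can be an AE | can be an AE |
| Arm known | can be an AE | cannot be attributed to daridorexant, so not an AE |

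SAEs follow, because an SAE must first be an AE.

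**Step 5: whether any other section closes the gap.** The sections on recording, on reporting SAEs, on safety monitoring (16) and on data analysis (17) were read for a rule that classification precedes disclosure or is made by a blinded person. There is none.

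**Step 6: the withdrawal rules.** Section 9 withdraws every subject whose code is broken. Section 13 says subjects are removed only for SAEs. By Step 4, a placebo emergency may fail to be an SAE and yet lead to withdrawal, so the two rules conflict for that subject.

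**Step 7: illustration of size.** Inputs: 12 planned completers and three subjects per arm in each block of six (section 16), giving 12 / 2 = 6 per arm. Assumption: one emergency in each arm.

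- Classified blind: 1/6 against 1/6, or 16.7% in each arm.
- Placebo event dropped after disclosure: 1/6 against 0/6, or 16.7% against 0%.
- Shift per reclassified event: 1/6 = 16.7 percentage points.

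A subject whose code is broken is withdrawn and so is not a completer. If that subject is counted in addition to six completers, the shift is 1/7 = 14.3 points. In general it is one divided by the number counted in the arm.

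**The case against.** The strongest reply is that the written order is the safe one. The attribution opinion comes before the call to IDS, it may come from the primary medical team rather than the PI, and the code-break paragraph describes no judgement afterwards. This stands as far as it goes. A reader might infer that the protocol directs the study team to open the code and then decide attribution; it does not say that. What remains is that the earlier opinion uses a weaker standard, is not listed in the AE record and does not fix AE status.

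A second reply is that no event disappears. Every code break goes to the RSRB and DSMB whatever the arm, Aim 4 covers all potential AEs and SAEs, and there are daily interviews and chart review. This also stands. A reader might infer that placebo emergencies would be hidden from oversight, and the documents do not support that. But reporting a code break does not place the event in the AE count.

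A third reply is that this protocol describes no between-arm safety test, that section 17 says only that these data will be collected, and that few code breaks are likely among at most 16 subjects. That limits the consequence. It does not remove it, because safety is a primary outcome and the counts are meant to inform the next trial.

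**Conclusion.** The point holds in a narrow form. The protocol lets AE and SAE status be settled after the arm is known, by staff it says must be blinded, under a definition that a known placebo subject can hardly meet. The text permits arm-dependent classification; it does not instruct it. The gap comes from the AE definition combined with the missing rule on when to classify, not from the code-break sentence alone.

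The size is 16.7 points per reclassified event with 6 per arm, or 14.3 with 7. This rests on assumed event counts and on an even split of completers. The likely frequency is low, and the correction is worth making because it is cheap.

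Two further inferences are tempting but should not be drawn:

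- **That later delirium ratings are compromised because the PI supervises them.** Section 8 says only that a psychiatrist supervises, and does not name the PI in that role.
- **That the published block size of six unmasks the rest of a block.** One disclosed assignment raises the chance that another given subject in the block is in the opposite arm from 50% to 3/5 = 60%. That is a small shift, and the case does not depend on it.

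**What to change.** 1. **Section 9, Plan for breaking the blind:** have IDS release the code to the treating clinician by default. The PI, coordinator and raters stay blinded unless they need to know. Emergency access is unchanged and must not wait for any form.
2. **Section 9, Recording adverse events:** add an entry for relationship to study agent. Require AE status, severity, seriousness and that relationship to be entered and time-stamped before the study team learns the arm.
3. **Section 9, Adverse event definition:** refer to receipt of study agent (daridorexant or placebo), so that the same event can qualify in either arm. Bring the SAE item that names a reaction to daridorexant into line.
4. **Sections 9 and 13:** reconcile the rule that withdraws every unblinded subject with the rule that limits removal to SAEs. Which of them should govern is for the investigators to decide.

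The cost is wording in these subsections, one entry on the AE form and an instruction to IDS. The drawback is that the PI, who is also the Data and Safety Monitor, learns the arm later than now. The need-to-know exception and the existing report of every code break to the RSRB and DSMB limit that drawback.
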